4.2. Exclusion Criteria

Any subject who meets one or more of the following criteria will be excluded from participation:

1. FEV1/FVC <70%
2. Requires supplemental oxygen therapy at rest.
3. History of other interstitial lung diseases including but not limited to radiation, drug toxicity, sarcoidosis, hypersensitivity pneumonia, bronchiolitis obliterans or organizing pneumonia.
4. History of clinically significant environmental exposure known to cause pulmonary fibrosis, including but not limited to drugs (e.g. methotrexate or amiodarone), asbestos, beryllium, radiation and domestic birds.
5. History of other medical conditions that are known or may result in interstitial lung disease. For example, any connective tissue disease including but not limited to scleroderma, polymyositis/dermatomyositis, systemic lupus erythematosus and rheumatoid arthritis.
6. AST, ALT or total Bilirubin >2 × ULN

7. Creatinine Clearance (CrCl) <30 mL/min/1.73 m², calculated using the Modification of Diet in Renal Disease estimated Glomerular Filtration Rate (MDRD eGFR).
8. Significant polycythemia defined as hemoglobin value >18 mg/dL.
9. ECG with a QTcF >450 ms (males) or QTcF >470 ms (females).
 - If ventricular pacing is noted on ECG, then QTcF intervals will not be calculated
10. Family or personal history of congenital long QT syndrome.
11. Female who is breast-feeding or pregnant.
12. Known current malignancy or current evaluation for a potential malignancy or history of malignancy within the past 2 years prior to screening, except for appropriately treated non-melanoma skin carcinoma, carcinoma in situ of the cervix, or Stage 1 uterine cancer.
13. Subject has used any of the following therapies within 30 days of screening:
 - Any cytotoxic, immunosuppressive or cytokine-modulating therapy including but not limited to: azathioprine, bosentan, ambrisentan, cyclophosphamide, cyclosporine, etanercept, iloprost, infliximab, leukotriene antagonists, methotrexate, mycophenolate, tacrolimus
 - Imatinib mesylate, Interferon gamma-1b, tyrosine kinase inhibitors (excluding nintedanib)
14. Pulmonary hypertension requiring active therapy including but not limited to endothelin receptor inhibitors or PDE inhibitors (e.g., sildenafil, tadalafil).
 - Note: intermittent use of a PDE inhibitor for erectile dysfunction may be allowed after approval by the Medical Monitor.
15. Hospitalization due to an exacerbation of IPF within 30 days of screening.
16. Subject plans to begin or has commenced pulmonary rehabilitation within 30 days of screening
 - Subjects on a stable exercise regimen at screening or whose regimen, in the opinion of the investigator, is not expected to change at any time during the entire study will be considered eligible for the study
17. Corticosteroids (>10 mg per day of prednisone or an equivalent) within 30 days of screening.
18. Current smoker (including use of eCigarettes or vaporizing) or history of smoking within 3 months from screening.
19. Clinical evidence of active infection, including but not limited to bronchitis, pneumonia, sinusitis, urinary tract infection or cellulitis, within 14 days of screening.
20. Active tuberculosis requiring treatment within the last 12 months.
 - Testing for latent tuberculosis is not required
21. Currently or, in the opinion of the investigator, soon to be listed for lung transplant.

22. History of unstable or deteriorating cardiac or pulmonary disease (other than IPF) within 6 months of screening including but not limited to the following:
 - Unstable angina pectoris or myocardial infarction or elective coronary intervention
 - Congestive heart failure requiring hospitalization
 - Uncontrolled clinically significant arrhythmias
23. Any condition possibly affecting drug absorption, such as previous surgery on the stomach or small intestine.
24. Participated in another clinical trial of an investigational drug (or medical device) within 30 days or 5-half-lives, whichever is longer, prior to screening, or is currently participating in another trial of an investigational drug (or medical device).
25. Known hypersensitivity to any component of the study drug.
26. Subject who, for any reason, is deemed by the investigator to be inappropriate for this study; or has any condition (such as addictive or psychosocial issues) which would confound or interfere with the evaluation of the safety, tolerability, or PK of the investigational drug; or is unable to comply with the study protocol.
27. History of mental illness within the last 5 years, unless the subject fulfills one of the following conditions:
 - The subject has not required or been prescribed any psychiatric medication (including but not limited to antidepressants or anxiolytics) within 12 months before screening and, in the opinion of the investigator, the subject is able and safe to participate in the study
 - The subject has been on a fixed regimen of psychiatric medications for at least 6 months before screening and displays no sign of acute mental illness and, in the opinion of the investigator, the subject is able and safe to participate in the study

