1.5.2. Pharmacokinetic Parameters

The mean PK results of GBT440 from analyzed samples to date, derived from whole blood concentration-time profiles, shows that both C_{max} and AUC increased proportionally with study drug dose for both single or multiple doses. The exposure of GBT440 at steady-state was consistent with accumulation predicted based on the single dose data.

For the same dose, GBT440 exposure was lower and the $T_{1/2}$ was significantly shorter in subjects with SCD compared with healthy subjects. At steady-state, the exposure in subjects with SCD was also lower than that observed in healthy subjects. Since IPF patients will most likely have hematocrit values within the normal range, PK of GBT440 in these patients are expected to be similar to that of healthy volunteers. Please refer to the GBT440 IB for additional details of GBT440 PK parameters.

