5.4.1.1. Hematology

Hematology assessments will include red blood cells (RBCs), hematocrit, hemoglobin, platelets and white blood cells (WBCs) with differential (basophils, eosinophils, neutrophils, monocytes and lymphocytes). Reticulocyte count and serum erythropoietin will also be collected.

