11.1. Sample Size

The sample size in this initial study was not selected based on statistical considerations but to determine preliminary safety, tolerability, PK, laboratory and clinical effects of GBT440 in IPF subjects.

The study will enroll approximately 33 subjects: approximately 18 subjects in Part A and approximately 15 subjects in Part B.

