13.2. Data Collection

The investigator will be responsible for maintaining accurate and adequate case records (source documents) from which data will be transcribed (or if electronically captured [EDC] source data, transferred) to CRFs designed to record data pertinent to this study. All relevant observations and data related to the study will be so recorded. This will include medical and medication history, physical examinations, a checklist of inclusion and exclusion criteria, investigational treatment administration, and a record of sample collection, clinical assessments, AEs, and final evaluation. The clinical site Clinical Research Associate (CRA) will review all CRFs and compare data to that contained in clinic notes and subjects' source documents/medical records.

Data collected for each subject will be entered into the CRF. The investigator will be responsible for the timeliness, completeness, and accuracy of the documentation entered into the CRFs.

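### Exclusion criterion 8 sets the polycythemia limit at hemoglobin above 18 mg/dL; the unit should evidently be g/dL, a factor of 1000

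*Protocol*

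**What the plan says.** Criterion 8 in Protocol Section 4.2 reads "Significant polycythemia defined as hemoglobin value >18 mg/dL". The exclusion list in the protocol synopsis has the same words, number and unit.

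Section 4.2 opens with the rule that gives each criterion its force: "Any subject who meets one or more of the following criteria will be excluded from participation". A single criterion is therefore enough to exclude a subject.

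Nothing elsewhere supplies a different unit for this limit. Protocol Section 5.4.1.1 lists hemoglobin in the hematology panel without a unit: "Hematology assessments will include red blood cells (RBCs), hematocrit, hemoglobin, platelets and white blood cells (WBCs) with differential". The SAP does not restate the eligibility criteria. Protocol Section 1.5.2 indicates the population expected: "Since IPF patients will most likely have hematocrit values within the normal range".

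**The concern.** The number 18 is a plausible limit for high hemoglobin in g/dL. In mg/dL it lies far below any hemoglobin a subject could have. The criterion as written therefore contradicts its own label: it claims to identify polycythemia but describes everyone, including the subjects with normal hematocrit whom Section 1.5.2 expects to enrol.

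The stakes are modest. This is an eligibility limit that sites must apply, not background text. Protocol Section 13.2 requires case records to include "a checklist of inclusion and exclusion criteria", and SAP Section 11 plans a listing of eligibility violations. Applied to the letter, that listing would contain every enrolled subject under criterion 8. Hemoglobin also matters for safety in this trial, because Protocol Section 1.5.4.1 names erythrocytosis among the signs of tissue hypoxia to be monitored. The entry limit for that parameter should be correct on the page.

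**Working it through.** There is no calculated figure in the plan to reproduce. The check is a unit conversion followed by applying the criterion under each unit.

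**Inputs**
- Limit as written: above 18 mg/dL (Protocol synopsis and Section 4.2, criterion 8).
- Rule: one criterion met means exclusion (Section 4.2, opening sentence).
- Conversion: 1 g/dL = 1000 mg/dL = 10 g/L.
- Hemoglobin range: 3 to 20 g/dL. This is an assumption made wide on purpose; the documents give no range.

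**Conversion**
- As written: 18 / 1000 = 0.018 g/dL, and 0.018 × 10 = 0.18 g/L.
- With g/dL: 18 × 1000 = 18,000 mg/dL, and 18 × 10 = 180 g/L.
- Ratio of the two limits: 18,000 / 18 = 1000.

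**Criterion applied to illustrative values**

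| Hemoglobin (g/dL) | In mg/dL | Excluded as written (>18 mg/dL) | Excluded with g/dL (>18 g/dL) |
|---|---|---|---|
| 3 | 3,000 | yes | no |
| 5 | 5,000 | yes | no |
| 12 | 12,000 | yes | no |
| 16 | 16,000 | yes | no |
| 17.9 | 17,900 | yes | no |
| 18.1 | 18,100 | yes | yes |
| 20 | 20,000 | yes | yes |

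The lowest assumed value is 3,000 / 18 ≈ 167 times the written limit and the highest is 20,000 / 18 ≈ 1,111 times. The choice of range therefore does not matter: every value is excluded as written. With g/dL, only values above 18 are excluded, which is how a polycythemia criterion should behave.

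**Direction of the error**

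The written limit is lower than the evident one, so every subject excluded at 18 g/dL is also excluded at 18 mg/dL. The slip cannot let in a subject whom the criterion was meant to keep out.

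**Effect on the analysis**

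The Safety and Efficacy-Evaluable populations (SAP Sections 9.1 and 9.2) are defined by receipt and duration of study drug, not by hemoglobin at entry. No sample-size calculation depends on the limit, since Protocol Section 11.1 states: "The sample size in this initial study was not selected based on statistical considerations". The statistical effect is nil.

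**The case against.** The strongest reply is that this is a proofreading slip without consequence. The label fixes the meaning for any clinician reading a hemoglobin result, and no site would apply a limit of 0.018 g/dL. Protocol Section 1.5.3 reports 16 Part A subjects who completed 15 days of dosing, so enrolment went ahead. With normal hematocrit expected, few subjects would come near even the intended limit. Most of this stands, and it is why the point is minor. It does not make the text correct.

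Two further cautions are fair. Part A dosing does not prove that sites read this wording as g/dL, because the protocol version those subjects enrolled under is not available; it only makes that reading likely. The eligibility checklist and the study manuals are not available either, so they may already carry the right unit. The documents therefore show an error in the protocol text but not that sites lack a correct working limit.

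Finally, g/dL is inferred from the size of the number and the purpose of the criterion. It is by far the most plausible reading, but the sponsor should confirm it.

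**Conclusion.** The concern holds. Criterion 8 is wrong as written in both places where it appears, by a factor of 1000, and nothing in the protocol or SAP corrects it. Read literally it would exclude all of the approximately 33 planned subjects (18 in Part A plus 15 in Part B). Read as evidently intended, it excludes only those above 18 g/dL.

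That the written limit excludes everyone needs no assumption beyond subjects having hemoglobin above 0.018 g/dL. That g/dL was meant is an inference. The likely practical harm is low, and this belongs at the lowest level of severity: worth correcting because it is an operative limit, but no threat to the trial's conclusions.

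**What to change.** Replace mg/dL with g/dL in exclusion criterion 8, in both the synopsis and Section 4.2, keeping the number 18, once the sponsor has confirmed the unit. Check that the eligibility checklist carries the same corrected limit, and use it when eligibility violations are identified for the SAP Section 11 listing.

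The cost is one unit changed in two places, by clarification letter to sites or at the next amendment. Design, data collection and analysis stay as they are.

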5. STUDY PROCEDURES AND EVALUATIONS

5.1. Subject Screening

The subject must be willing and able to sign and date the informed consent form (ICF) before any screening procedures or study-specific tests may be performed. The baseline 6MWT performed at screening must be performed within 7 days of the Day 1 visit. If the 6MWT falls outside of the 7-day window, it must be repeated (the repeat may occur at the time of the Day 1 visit prior to any Day 1 visit assessments).

All subjects who sign the informed consent will be given a unique study number. This number will be used to identify the subject throughout the clinical study and must be used on all study documentation related to that subject.

The screening period for a particular subject commences at the point at which the subject undergoes the first study-specific screening assessment and must be completed and evaluated (refer to [Appendix A](#)), prior to any Day 1 visit assessments.

Subjects may be rescreened up to two times, if deemed appropriate by the Principal investigator. The rescreening visit should not occur sooner than 10 calendar days after the failed screening visit.

5.2. Avoidance of Pregnancy

Women of Child-Bearing Potential

Pregnancy should be avoided by either absolute abstinence or the use of highly effective means of contraception (refer to [Section 8.6](#)) for the duration of the study and a total period of 3 months after the subject has taken the last dose of GBT440.

Female subjects who become pregnant during the study will have study drug discontinued but continue in the study to complete all safety follow up assessments (refer to [Section 6.3](#)).

Women of Non Child-Bearing Potential

Female subjects of non-child-bearing potential are defined as; bilateral oophorectomy, hysterectomy or post-menopausal females being amenorrhoeic for at least 2 years.

For female subjects who report surgical sterilization (i.e., hysterectomy and/or bilateral oophorectomy), surgical sterilization procedures should be supported with clinical documentation and noted in the Relevant Medical History/Current Medical Conditions section of the CRF.

Instructions for Male Subjects

There is no information about effects that GBT440 could have on the development of the fetus in humans. Therefore, it is important that the partners of male subjects do not become pregnant during the entire study and for a total 3 months after the male subject has taken the last dose of GBT440.

All male subjects should use the methods of contraception as outlined in [Section 8.6](#).

5.3. Clinical Assessments

Screening assessments must be performed and evaluated prior to randomization on Day 1. This study has nine visits in total including the screening visit and patients will be enrolled for approximately 58 days from the time of randomization until the last study visit. The timing of the visits, associated visit windows and all assessments are outlined in [Appendix A: Schedule of Study Assessments](#).

5.3.1. Medical History and Demographic Data

Medical history includes clinically significant diseases, surgeries, cancer history (including prior cancer therapies and procedures), inflammatory/autoimmune disease, smoking history, use of alcohol and drugs of abuse within the previous year, and IPF-associated conditions including but not limited to pulmonary hypertension, familial IPF and gastroesophageal reflux disease. Medical conditions that are a result of side effects from concomitant medications should be clearly defined and entered into the eCRF.

Any medical condition present at baseline should be followed during the study and a change from the baseline status (intensity or frequency) should be reported as an adverse event if deemed clinically significant by the investigator (refer to [Section 10](#)).

All concomitant medications (e.g., prescription drugs, over-the-counter drugs, herbal/homeopathic remedies, nutritional supplements) used by the patient within 30 days prior to the Screening visit should be entered on the Concomitant Medications eCRF. A start date should be entered for all medication items entered into the Concomitant Medications eCRF, including those medications used chronically.

Demographic data will include age (date of birth), sex, and self-reported race/ethnicity.

5.3.2. Physical Examination

A complete physical examination should include the following: an evaluation of the head, eyes, ears, nose, throat, and the cardiovascular, dermatological, musculoskeletal, respiratory, gastrointestinal, and neurological systems. A rectal or pelvic examination is not required. Any abnormality identified during screening should be recorded on the eCRF.

At subsequent visits, limited, symptom-directed physical examinations should be performed. Changes from baseline abnormalities should be recorded in the patient notes. New or worsened abnormalities should be recorded as adverse events on the Adverse Event eCRF.

Vital signs will include measurements of respiratory rate, pulse rate, body temperature, systolic and diastolic blood pressure and SpO₂ by pulse oximetry. Blood pressure and SpO₂ measurements should be taken while the patient is in a seated or semi-recumbent position, and resting for at least 5 minutes.

5.4. Laboratory Examination

5.4.1. Clinical Laboratory Studies

It is the responsibility of the Investigator to assess the clinical significance of all abnormal clinical laboratory values as defined by the list of normal values on file for the local clinical

laboratory. All clinically significant laboratory value abnormalities are to be recorded as AEs.

For the purpose of this study, a clinically significant laboratory value will be any abnormal result that, in the judgment of the Investigator, is an unexpected or unexplained laboratory value or if medical intervention or corrective action is required. Any abnormal values that persist should be followed at the discretion of the Investigator.

Please refer to [Appendix A](#) Schedule of Study Assessments for all time points.

5.4.1.1. Hematology

Hematology assessments will include red blood cells (RBCs), hematocrit, hemoglobin, platelets and white blood cells (WBCs) with differential (basophils, eosinophils, neutrophils, monocytes and lymphocytes). Reticulocyte count and serum erythropoietin will also be collected.

5.4.1.2. Blood Chemistries

Blood chemistry assessments will include measurement of albumin, bicarbonate, blood urea nitrogen (BUN), calcium, chloride, creatinine, creatine kinase, glucose, lactate dehydrogenase, magnesium, phosphorus, potassium, sodium, total protein, and uric acid.

5.4.1.3. Liver Function

Liver function assessments will include measurements of serum alanine aminotransferase (ALT), aspartate aminotransferase (AST), alkaline phosphatase, gamma glutamyl transferase (GGT), and total bilirubin (direct and indirect).

5.4.1.4. Urinalysis

Urine will be assessed for color and appearance. Dipstick analysis for specific gravity, pH, protein, glucose, ketones and occult blood and microscopic analysis (RBCs, WBCs, bacteria and casts) will be performed.

5.4.1.5. Electrocardiograms

12-lead ECGs should be performed after the subject has been resting in a supine or semi-recumbent position for at least 5 minutes and prior to all other non-PRO assessment. The ECGs will be collected in triplicate. Three separate recordings approximately 1 minute apart should be performed. All three tracings must be stored at the study site. If ventricular pacing is noted on ECG, then QTcF intervals will not be calculated.

5.4.1.6. Other Clinical Laboratory Tests

Screening tests will include serology for hepatitis A (IgM anti-HAV), hepatitis B surface antigen (HBsAg), hepatitis C (HCV) and HIV-1/0/2 antibodies if there is no documented testing results within 3 months of screening.

For women of child bearing potential, a pregnancy test (serum HCG) will be performed at screening and urine pregnancy testing will be performed during the study. If the urine pregnancy test is positive the result must be confirmed with a serum pregnancy test.

Coagulation (Panel) including PT, PTT and INR will be collected at screening and Day 28.

5.5. Disease Related Evaluations

5.5.1. Spirometry and Diffusing Capacity of the Lung for Carbon Monoxide (DL_{CO})

All equipment, procedures, and personnel qualifications for the assessment of lung function should be based on the recommendations of the American Thoracic Society ([ATS 2005](#)) and will be performed at each site using local equipment and procedures.

Spirometry measurements will include FVC, FEV₁, DL_{CO} and other measures per the site's local practices. Post-bronchodilator assessments will not be performed.

DL_{CO} will be measured at each site by determining the diffusing/transfer capacity of the lung for carbon monoxide.

Spirometry and DL_{CO} should be performed at each scheduled visit at approximately the same time of day (e.g. in the morning) and before the 6MWT, if scheduled on the same visit day.

Local reports from the spirometry and DL_{CO} testing will be stored on site.

5.5.2. Oxygen Saturation

During screening and with all scheduled vital sign assessments resting, room air oxygen saturation (SpO₂) will be measured by pulse oximetry (provided by the Sponsor) whilst the subject is seated and resting for at least 5 minutes. Before recording the SpO₂ value in the eCRF the study staff should ensure the measurement is stable, which may require continuous or repeated measurements and ensuring the subject is resting.

SpO₂ will be also be collected at baseline, during and following completion of the 6MWT and cardio-pulmonary exercise testing.

5.5.3. 6-Minute Walk Test (6MWT)

Functional exercise capacity will be evaluated at Baseline and Days 15, 28 and 58 using the 6-minute walk test. The 6MWT will be performed without the subject using supplementary oxygen. Oxygen may be used at any time during the 6MWT, if in the opinion of the Investigator or testing technician it is required for safety reasons. The 6MWT should then be stopped.

The baseline 6MWT performed at screening must be performed within 7 days of the Day 1 visit. If the 6MWT falls outside of the 7-day window, it must be repeated (the repeat may occur at the time of the Day 1 visit prior to any Day 1 visit assessments).

Guidelines developed by the ERS/ATS will be used for conducting the test and interpreting the results ([ATS 2002](#) and [Holland 2014](#)). Instructions for the conduct of the 6MWT will be provided in a separate manual.

The 6MWT should be performed at each scheduled visit at approximately the same time of day (e.g. in the morning) and after spirometry and DL_{CO} assessments (if scheduled on the same Visit day).

As part of the 6MWT, SpO₂, heart rate and the Borg dyspnea scale will be measured at the following time points: prior to starting the test, during the test, at completion of the test, 1 minute and 2 minutes after test completion.

For safety reasons, all patients should be clinically stable prior to performing the 6MWT.

Absolute contraindications to the 6MWT include unstable angina or myocardial infarction during the previous month.

Relative contraindications to participation in the 6MWT include:

- Resting heart rate >120 or <60 beats per minute
- Systolic blood pressure >180 mmHg
- Diastolic blood pressure >100 mmHg

